After administering the consent quiz during the confirmation call, study staff will answer questions, review next steps, and clarify expectations. If a potential participant did not pass the consent quiz, study staff will be able to review the appropriate consent form sections and to re-administer the consent quiz. After completing the confirmation call, all eligible study participants will be considered enrolled into the study. Study staff will send via email secure Survey Gizmo links with the HIPAA authorization form, locator form and baseline survey. The HIPAA authorization form will now have an option for "I'm not sure." If someone selects the not sure option, they will be directed to call the study number to discuss their concerns or ask questions before moving forward in the enrollment process. Participants must agree to the HIPAA authorization to continue with the study. After agreeing to the HIPAA authorization, participants will click the next step link to complete the locator form. After completing the locator form, participants will click a link to complete the baseline survey. The brief locator form will request important contact information in order to locate participants for the follow-up survey and to re-engage with research and intervention activities, if needed. For participants who report they share their email address with someone else, we will ask them if they are sure it is okay for us to send information to this email address. If they say No or Prefer not to answer, they will be asked if they have a secondary email address they want to use. If someone does not complete the locator form or baseline survey, study staff will reach out to the participants to encourage them to complete these required activities. All participants will have one week to complete the enrollment process. Randomization will occur after completing the baseline survey. We will use block randomization to assign a group of three participants to each condition. We will wait till we have at least people randomized to Program A to begin the program. Participants will be informed of their assigned group after completing their baseline survey. WTV will notify participants of their randomly assigned program and the appropriate next steps for their specific program assignment. This change will allow us to conduct block random assignment computed by [name] and to allow us to equal number of people in each group throughout the study recruitment period. We will program Survey Gizmo to send the research team an automatic email when someone completes the baseline survey.

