
When Program A reaches approximately nine participants, we will form the next group assigned to Program A. We will follow-up participants who have incomplete digital data collection that occurs after consent for up to two times.

Figure A: Recruitment and Enrollment Flowchart

Recruitment activities will be conducted after IRB approval through March 31, 2020 or until we recruit up to 84 eligible CSOs, whichever comes first. We will track and document which recruitment strategies yield the best engagement. Please see examples of images and messaging we will use for different methods of recruitment. We plan to implement the following recruitment methods:

a. Recruitment channels

i. Participants will be recruited through the following methods as needed:

1. WTV Promotions (e.g., website callouts, emails, social media posts and 1:1 message) to existing and future WTV members.
2. Engagement of the membership group to suggest a friend and make a referral if they know anyone who fits the participant description.
3. Reaching out to existing partners who provide services to patients with OUD.
 - a. Sixth Street Community Center
 - b. Tempest
 - c. Rebel For A Change
 - d. Best Day Ever
 - e. Center for Motivation and Change

- f. JoinGroups.Com (medication-assisted treatment (MAT) for opioid addiction)
- 4. Develop recruitment strategies to increase diversification of study participants
 - a. Promote research study on the following professional counseling member websites:
 - i. Association of Black Psychologists (ABPsi)
 - ii. National Association of Black Social Workers (NABSW)
 - b. Develop new partnerships with providers who serve more diverse populations, including communities of color and lower SES
- 5. Targeted digital and local advertising efforts.
 - a. Facebook
 - b. Instagram
 - c. Google

3.3 Describe how prospective participants will be screened. Include information about: how, when, where, and by whom (by position or role, not by name). Describe any instruments that will be used or tests that will be performed during the screening process.

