Participant assigned to the CRAFT-A (Program A) and CRAFT-C (Program B) groups will have access to a 12-module on-line CRAFT intervention and asked to complete one module weekly for 12 weeks. Modules introduce CRAFT concepts and provide workbooks to assist participants in learning and applying the concepts. The modules include: 1) Introduction to CRAFT; 2) Communication Training; 3) Functional Analysis of Drug Using; 4) Positive Reinforcement; 5) Withdrawing Reinforcement; 6) Allowing Natural Consequences; 7) Problem-solving; 8) Life Enrichment; 9) Suggesting Treatment; 10) Recovery and Relapse; 11) Relationship; and 12) Recap of Skills. CRAFT-A participants also attend a weekly 60-minute online group sessions facilitated by a CRAFT-certified coach. CRAFT-C participants attend a weekly 60-minute individualized on-on-one coaching session with a CRAFT-certified coach. During weekly group or individual sessions concepts are briefly reviewed, questions are answered, and skills are practiced through role-plays of common situations. One-on-one sessions involve role-plays that are tailored to the participants' specific circumstances.

Counselors must complete their CRAFT training and certification prior to implementing Program A and Program B. In addition, CRAFT counselors must complete CITI training as limited personnel.

STUDY ACTIVITIES BY PROGRAM		
Experimental Programs		Standard Care Program
Program A & Program B		Program C
● Commit 1½ to 1¾ hours a week	● Commit 1 to 1½ hours a week	
● Watch a 12-module online support program delivered weekly	● Join a private online support forum for people with a loved one with an opioid use problem	
● Each module will be 30 to 45 minutes in length	● Gain access to knowledge and experiences of fellow CSOs shared in peer-led forum discussions	
● Attend weekly 60-minute online sessions facilitated by a CRAFT coach via Zoom or phone	● Post your own questions specific to your current situation and receive support from peers and WTV moderators	
● Review content from the weekly module	● Share your knowledge and experience to answer fellow CSOs' questions and to support others through their journey	
● Participate in a Question and Answer segment		
● Practice content with role-plays		
Program A		Program C
● Weekly sessions are in a small group with WTV coach and 3 to 8 study participants using Zoom	● Weekly sessions are one-to-one with WTV coach using Zoom	● Discussions are self-initiated and ongoing

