Yes. CSOs who become pregnant during the study will be able to continue. The proposed study is a behavioral health intervention and is conducted online. We do not expect pregnant participants to require additional accommodations because they can participate via a smartphone or computer at any location.

9.6 Describe the potential direct benefits to individual participants or to others as a result of study participation. Indicate if there may not be any direct benefits to participants or to others.

Participants may not receive direct benefits from this study; however, the study uses teaching approaches when delivered face-to-face have been shown to help people interact with their loved ones using healthier strategies. In addition, participants may feel more supported by engaging with other CSOs or by interacting with their coach, depending on their assigned group. Current WTV members have reported increased level of happiness, support, and healthy behaviors.

9.7 Define reportable and non-reportable Adverse Events (AEs).

Reportable AEs:

Will be defined as: significant discomfort from answering research questions or participating in the treatment intervention such that the participant decides to stop their participation, reports of new diagnoses of

depression, anxiety, or panic attacks. In addition, we will document reports from the CSO of domestic or intimate partner violence that may occur during their time in the study. We plan to collect reportable AEs that occur for the participant.

Non-reportable AEs:

Clinically insignificant events are not considered AE's. Examples of clinically insignificant events include mild viral illness (e.g., colds, flu, and runny nose), common headaches, minor scratches, and mild symptoms or problems associated with medical conditions or accidents not related to drug use (e.g., back pain). As per the definition of AEs, only significant worsening of psychiatric problems or new problems will be reported as AEs. We will monitor attrition rates but drop out from the study will not be reported as an AE.

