All WTV and PHMC staff who interact with participants or monitor online conversations will be trained on the definitions of reportable and non-reportable AEs and SAEs and the way to complete the forms reporting them. The PI and Co-I will monitor the WTV forum and meet regularly with CRAFT counselors to track and to document any AEs and SAEs. The WTV clinical team will be interacting with participants in the CRAFT interventions on a

regular basis and will be responsible for collecting AE and SAE information shared during their interactions and reporting them to the PHMC team. In addition, the research assistant will document information related to AEs and SAEs shared when contacting participants. Also, the WTV team monitor online comments and interactions and will report any AEs or SAEs reported there to the PHMC team.

All adverse and serious adverse events occurring during the study are documented on a form, reviewed and signed by [name] and the PI, [name], and reported to the IRB. All SAEs are reported to the IRB within 48 hours of our awareness of the event (24 hours for fatal events). A summary of all SAEs and AEs that occurred during six-month pilot study will be included in any progress reports to the IRB. We will begin to collect AE and SAE information between the first intervention session and their 12-week post enrollment assessment.

9.10 Will you submit or have you submitted the protocol for additional oversight by a Data and Safety Monitoring Board (DSMB)?

Yes:

- The protocol will be submitted to PHMC's DSMB.
- PHMC's DSMB conducted the initial review on November 15, 2019.
- The protocol will be submitted to an external DSMB.
- An external DSMB or monitoring committee has reviewed the study. All reports are attached.
- No, a DSMB is not needed for this study

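### The dated adverse-event window in Protocol 9.9 can close before the 12 weekly CRAFT sessions are finished, mainly in CRAFT-A, and conflicts with undated duties in the same section

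*Protocol*

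**What the plan says.** The Protocol's only dated rule for safety data is in section 9.9: "We will begin to collect AE and SAE information between the first intervention session and their 12-week post enrollment assessment". It answers the form's request for the start and end of collection.

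The timing of exposure is set elsewhere:

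- **Enrollment (section 3.2).** "After completing the confirmation call, all eligible study participants will be considered enrolled into the study". The HIPAA form, locator form and baseline survey follow, and "All participants will have one week to complete the enrollment process".
- **Allocation (section 3.2).** "Randomization will occur after completing the baseline survey", so it comes after the confirmation call.
- **Group formation, CRAFT-A only (section 3.2).** The start is held until a minimum number has been randomized to Program A; the number itself is absent from the text. The section then says: "When Program A reaches approximately nine participants, we will form the next group assigned to Program A". The activity table in section 4.1 gives 3 to 8 participants per group.
- **Length of the program (section 4.1).** Participants in both CRAFT arms "will have access to a 12-module on-line CRAFT intervention and asked to complete one module weekly for 12 weeks", with a coached session each week.

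Section 9.9 also contains sentences with no end date for a participant. The clinical team is to collect and pass on events that come up in its contacts with participants, all events during the study are to be documented, and progress reports are to summarize events over a pilot of six months.

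**The concern.** The window's two ends are counted from different origins. Its length in weeks of exposure therefore shrinks by one week for each week between enrollment and the first session. The sessions that drop out are always the last ones. In the module list of section 4.1, the last four cover suggesting treatment, recovery and relapse, the relationship, and a recap.

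The harms that section 9.7 makes reportable can follow any session. They include discomfort from the intervention that leads a participant to stop. On partner violence the section says: "we will document reports from the CSO of domestic or intimate partner violence that may occur during their time in the study". A pilot should be able to describe safety over a complete delivered course. With the dated rule as written, a participant who starts late has no required collection for the end of the course, even though a coach is still meeting that participant weekly. Only CRAFT-A has a stated wait for a group, so the shortfall falls mainly there.

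**Working it through.** The plan gives no figure to reproduce. The check is timeline arithmetic.

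**Step 1: start delay and sessions outside.** Let D be the weeks from enrollment to session 1. Session k is held at week D + (k − 1), and the window closes at week 12. A session is outside when D + k − 1 > 12, that is, when k > 13 − D. Session 12 falls at week D + 11.

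| D (weeks) | Week of session 12 | Sessions outside |
|---|---|---|
| 0.5 | 11.5 | 0 |
| 1 | 12 | 0 |
| 2 | 13 | 1 |
| 3 | 14 | 2 |
| 4 | 15 | 3 |
| 6 | 17 | 5 |

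The threshold is D = 1 week. This step uses only the protocol's own timing and takes the assessment to fall at week 12.

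**Step 2: CRAFT-C.** There is no group wait. If session 1 is within one week of enrollment, nothing falls outside. If it is more than one and up to two weeks after, one session does.

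**Step 3: CRAFT-A.** The inputs below are assumptions except where a source is given.

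- Up to 84 participants (section 3.1) in three equal arms: 84/3 = 28 per arm.
- Even accrual over R weeks. Section 3.2 ends recruitment on 31 March 2020 but gives no start date. The DSMB review of 15 November 2019 (section 9.10) to that date is 137 days, or 137/7 = 19.6 weeks. I take R = 12, 19.6 and 26 to bracket it.
- No group starts before it is full, at g = 3, 8 or 9 members.
- A lag e from enrollment to assignment of 0.5 week, varied from 0 to 1.

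CRAFT-A gains one member every R/28 weeks. Member i of g has D = (g − i) × R/28 + e.

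Worked case, R = 19.6, g = 9, e = 0.5: R/28 = 0.70, so D = 6.1, 5.4, 4.7, 4.0, 3.3, 2.6, 1.9, 1.2, 0.5. Sessions outside are 6, 5, 4, 3, 3, 2, 1, 1, 0, which is 25 of 9 × 12 = 108. The first three members have all of modules 9 to 12 outside (for the third, 13 − 4.7 = 8.3).

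Share of CRAFT-A sessions outside the window, e = 0.5:

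| Group size | R = 12 | R = 19.6 | R = 26 |
|---|---|---|---|
| 3 | 2.8% | 5.6% | 8.3% |
| 8 | 12.5% | 19.8% | 28.1% |
| 9 | 13.9% | 23.1% | 31.5% |

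**Step 4: sensitivity to time zero.** Setting e = 0 treats enrollment as complete only at assignment. The ranges over R become 0% to 2.8% for groups of three and 10.2% to 25.9% for groups of nine. With e = 1 they are 5.6% to 8.3% and 17.6% to 33.3%. The CRAFT-A wait accounts for most of the effect in groups of eight or nine; in groups of three the result depends on the lag.

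**The case against.** **Late events are not simply lost.** A reader might infer that harms after week 12 go uncollected. The documents do not support that. Section 9.9 also makes the clinical team responsible for events shared in its interactions and has all events during the study documented, with no cut-off for either. Coaches still meeting a participant in week 14 could rely on those sentences. What stands is narrower: the one dated rule does not require collection after the 12-week assessment, and it conflicts with the undated duties beside it.

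**No single size can be given.** A reader might take 23% from the worked case as the effect. It depends on groups of nine starting only when full, yet section 4.1 allows at most eight. The sentence about nine may describe when a further group opens, and the minimum to start is missing. The accrual period is assumed, and 84 is an upper limit. Only the range is defensible.

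**Time zero is ambiguous.** Sections 4.1 and 6.2 place the HIPAA authorization within enrollment, and 4.1 also includes the baseline survey. Time zero may therefore be up to a week later than section 3.2 implies. This may remove the gap in CRAFT-C. It does not remove the CRAFT-A group wait.

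**The assessment has no stated visit window.** A late survey would extend collection for that participant. This is true, but it is accidental and cannot be relied on to cover the remaining sessions.

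**Bias between arms.** A reader might infer that CRAFT-A would look safer than CRAFT-C. The hypotheses and outcomes in sections 1.2 and 1.3 contain no between-arm safety comparison, and section 9.8 expects few or no serious events. That inference is not supported.

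**Conclusion.** The point holds as an internal inconsistency in section 9.9 with a practical consequence. By the protocol's own timing, any first session more than one week after enrollment leaves at least one coached session outside the dated window. This is likeliest in CRAFT-A, the only arm that waits for a group. Events after those sessions are not required to be collected by the dated rule, while neighbouring sentences suggest that they should be.

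Under even accrual of 84 over 12 to 26 weeks and a half-week lag, the affected share of CRAFT-A sessions is about 3% to 8% for groups of three and 14% to 32% for groups of nine. These figures show the possible scale; they are not forecasts, because accrual and group size are not fixed in the protocol. The threshold of one week does not depend on them. The gap is worth closing because the change is small and the coaches are already in contact.

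**What to change.** In section 9.9, reconcile the dated sentence with the undated ones so that AE and SAE collection runs through the later of the 12-week post-enrollment assessment and the participant's last program session. Coaches record events on the existing forms until that session. PEER has no sessions, so its window would still end at the assessment.

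The same edit should state which event counts as enrollment for the 12-week clock, since sections 3.2, 4.1 and 6.2 differ. The group-size statements in 3.2 and 4.1 also need to be reconciled with each other.

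The cost is a sentence or two of protocol text, with no new staff, visit or survey. The one drawback is that observation time will differ slightly between arms. Any by-arm AE summary should therefore state its window or be restricted to the common 12-week window.
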